6.5.4.4 Hepatotoxicity

Any liver event which meets the criteria for “**medically significant**” event as outlined in [Table 13-1](#) of [Appendix 9](#) should follow the **standard procedures for SAE reporting** as described in [Section 7.2](#).

6.5.4.5 Plasma Cortisol

Evening plasma cortisol will be measured at Visits 201, 207 and 214 and EOT if applicable. The sampling time point is shown in [Table 6-1](#) and [Table 6-2](#).

6.5.5 Electrocardiogram (ECG)

ECGs must be recorded after 10 minutes rest in the supine position to ensure a stable baseline.

When the ECG recording time coincides with vital signs, spirometry, and blood draws, the ECG must be performed first, followed by vital signs and the blood draws but with enough time planned to ensure the spirometry is performed at the planned time point outlined in [Table 6-2](#). Spirometry must be performed as close to the scheduled time point as possible.

Centralized ECG equipment

At Visit 101, a screening ECG will be measured to test for eligibility for trial inclusion. (Patients whose ECG is abnormal at screening due to technical/mechanical faults may be re-screened.) At Visits 102/201, 207, and 214, ECGs will be measured at -35min pre-dose (evening dose) and post dose 30 min/ 1 hour. At Visit 204 ECG will be measured pre-dose only as indicated in [Table 6-2](#). At Visit 210, the ECG will be done -35min pre-dose only. All electrocardiograms should include 12 standard leads. An ECG tracing will be taken for those patients who prematurely discontinue from the study treatment.

For each ECG performed original traces and should be printed. Each ECG will be sent electronically for central review directly from the ECG machine. One print-out will be generated and kept at the investigator site as source documentation and will be dated and signed. The subject's number, the date, actual time of the tracing, and Study Code must appear on each page of the tracing.

Full details of all procedures relating to the ECG collection and reporting will be contained in an investigator manual to be provided by the central laboratory to each investigator site. In the event that the central cardiologist reports that an ECG is abnormal, the investigator must assess whether the ECG abnormality is clinically significant or not. A clinically significant abnormality should be reported as an AE. If necessary a cardiologist may be consulted.

Clinically significant ECG findings at baseline must be discussed with the sponsor before administration with investigational treatment.

If a patient experiences a clinically significant change in cardiac rhythm or other clinically significant cardiovascular abnormality, the investigator should consider withdrawing the patient from the study.

Clinically significant abnormalities should be recorded on the relevant section of the medical history/Current medical conditions/AE CRF/e-CRF page as appropriate.

6.5.6 Serious Asthma outcomes

[figure not shown]
Asthma-related hospitalizations, asthma-related intubations or asthma-related deaths over the 52-week treatment epoch will be recorded and will all be reviewed by the Adjudication Committee. Hospitalization is defined as an inpatient stay or a ≥ 24 hour stay in an observation area in an emergency department or other equivalent facility.

6.5.7 Pregnancy and assessments of fertility

A plasma and urine pregnancy test will be performed in pre-menopausal women who are not surgically sterile (tests provided by the Central Laboratory) per Assessment Schedule [Table 6-1](#). If the urine pregnancy test at Visit 1, Visit 102 and Visit 207 is positive a plasma testing is to be done to confirm the pregnancy. A positive plasma pregnancy test at Visit 1, Visit 101, Visit 102, Visit 207 (Week 26), Visit 214 or EOT or at any time during the study requires the patient to be discontinued from the study treatment. Refer to [Section 5.4.9](#) and [Section 7.4](#) for more details. Additional pregnancy testing might be performed if requested by local requirements.

6.5.8 Appropriateness of safety measurements

The safety assessments selected are standard for this indication/patient population.

7 Safety monitoring

7.1 Adverse events

An adverse event (AE) is any untoward medical occurrence (i.e., any unfavorable and unintended sign including abnormal laboratory findings, symptom or disease) in a subject or clinical investigation subject after providing written informed consent for participation in the study. Therefore, an AE may or may not be temporally or causally associated with the use of a medicinal (investigational) product.

The occurrence of adverse events should be sought by non-directive questioning of the patient at each visit during the study. Adverse events also may be detected when they are volunteered by the patient during or between visits or through physical examination, laboratory test, or other assessments.

Abnormal laboratory values or test results constitute adverse events only if they fulfill at least one of the following criteria:

- they induce clinical signs or symptoms,
- they are considered clinically significant,
- they require therapy.

Clinically significant abnormal laboratory values or test results should be identified through a review of values outside of normal ranges/clinically notable ranges, significant changes from baseline or the previous visit, or values which are considered to be non-typical in patient with underlying disease. Investigators have the responsibility for managing the safety of individual patient and identifying adverse events.

Adverse events should be recorded in the Adverse Events CRF under the signs, symptoms or diagnosis associated with them, accompanied by the following information.

- The severity grade mild: usually transient in nature and generally not interfering with normal activities
- Moderate: sufficiently discomforting to interfere with normal activities
- Severe: prevents normal activities

- Its relationship to the study drug (s) (suspected/not suspected)
- Study treatment (no/yes), or
- Investigational treatment (no/yes), or
- The other study treatment (non-investigational) (no/yes) or both or indistinguishable,
- Its duration (start and end dates) or if the event is ongoing an outcome of not recovered/not resolved should be reported.
- Whether it constitutes a serious adverse event (SAE - See section 7.2 for definition of SAE)
- Action taken regarding the study treatment

All adverse events should be treated appropriately. Treatment may include one or more of the following:

- No action taken (i.e. further observation only)
- Study treatment dosage adjusted/temporarily interrupted
- Study treatment permanently discontinued due to this adverse event
- Concomitant medication given
- Non-drug therapy given
- Patient hospitalized/patient's hospitalization prolonged
- its outcome (not recovered/not resolved; recovered/resolved; recovering/resolving, recovered/resolved with sequelae; fatal; or unknown)

Once an adverse event is detected, it should be followed until its resolution or until it is judged to be permanent, and assessment should be made at each visit (or more frequently, if necessary) of any changes in severity, the suspected relationship to the study drug, the interventions required to treat it, and the outcome.

Information about common side effects already known about the investigational drug can be found in the Investigator Brochure (IB) or will be communicated between IB updates in the form of Investigator Notifications. This information will be included in the patient informed consent and should be discussed with the patient during the study as needed.

The investigator should also instruct each patient to report any new adverse event (beyond the protocol observation period) that the patient, or the patient's personal physician, believes might reasonably be related to study treatment. This information should be recorded in the investigator's source documents, however, if the AE meets the criteria of an SAE, it must be reported to Novartis.

7.2 Serious adverse events

7.2.1 Definition of SAE

An SAE is defined as any adverse event (appearance of (or worsening of any pre-existing) undesirable sign(s), symptom(s) or medical condition(s) which meets any one of the following criteria:

- is fatal or life-threatening

- results in persistent or significant disability/incapacity
- constitutes a congenital anomaly/birth defect
- requires inpatient hospitalization or prolongation of existing hospitalization, unless hospitalization is for:
 - routine treatment or monitoring of the studied indication, not associated with any deterioration in condition (specify what this includes)
 - elective or pre-planned treatment for a pre-existing condition that is unrelated to the indication under study and has not worsened since signing the informed consent
 - treatment on an emergency outpatient basis for an event not fulfilling any of the definitions of a SAE given above and not resulting in hospital admission
 - social reasons and respite care in the absence of any deterioration in the patient's general condition
- is medically significant, i.e. defined as an event that jeopardizes the patient or may require medical or surgical intervention.

All malignant neoplasms will be assessed as serious under “medically significant” if other seriousness criteria are not met.

Life-threatening in the context of a SAE refers to a reaction in which the patient was at risk of death at the time of the reaction; it does not refer to a reaction that hypothetically might have caused death if more severe (see [Annex IV, ICH-E2D Guideline](#)).

Medical and scientific judgment should be exercised in deciding whether other situations should be considered serious reactions, such as important medical events that might not be immediately life threatening or result in death or hospitalization but might jeopardize the patient or might require intervention to prevent one of the other outcomes listed above. Examples of such events are intensive treatment in an emergency room or at home for allergic bronchospasm, blood dyscrasias or convulsions that do not result in hospitalization or development of dependency or abuse (see [Annex IV, ICH-E2D Guideline](#)).

Any suspected transmission via a medicinal product of an infectious agent is also considered a serious adverse reaction.

All AEs (serious and non-serious) are captured on the e-CRF. SAEs are also required for individual reporting to DS&E as per [Section 7.2.2](#).

7.2.2 SAE reporting

To ensure patient safety, every SAE, regardless of causality, occurring after the patient has provided informed consent and until 30 days after the patient has stopped study participation (defined as time of last dose of study drug taken or last visit whichever is later) must be reported to Novartis within 24 hours of learning of its occurrence. Any SAEs experienced after the 30 days period should only be reported to Novartis safety if the investigator suspects a causal relationship to study treatment.

All follow-up information for the SAE including information on complications, progression of the initial SAE and recurrent episodes must be reported as follow-up to the original episode within 24 hours of the investigator receiving the follow-up information. An SAE occurring at a

different time interval or otherwise considered completely unrelated to a previously reported one must be reported separately as a new event.

Information about all SAEs (either initial or follow up information) is collected and recorded on the Serious Adverse Event Report Form, all applicable sections of the form must be completed in order to provide a clinically thorough report. The investigator must assess the relationship of each SAE to each specific component of study treatment, complete the SAE Report Form in English, and submit the completed form within 24 hours to Novartis. Detailed instructions regarding the submission process and requirements for signature are to be found in the investigator folder provided to each site.

Follow-up information is submitted as instructed in the investigator folder. Each reoccurrence, complication, or progression of the original event must be reported as a follow-up to that event regardless of when it occurs. The follow-up information should describe whether the event has resolved or continues, if and how it was treated, whether the treatment code was broken or not and whether the patient continued or withdrew from study participation. If the SAE is not previously documented in the Investigator's Brochure or Package Insert (new occurrence) and is thought to be related to the investigational treatment a Drug Safety and Epidemiology Department associate may urgently require further information from the investigator for Health Authority reporting. Novartis may need to issue an Investigator Notification (IN) to inform all investigators involved in any study with the same investigational treatment that this SAE has been reported. Suspected Unexpected Serious Adverse Reactions (SUSARs) will be collected and reported to the competent authorities and relevant ethics committees in accordance with EU Guidance 2011/C 172/01 or as per national regulatory requirements in participating countries.

7.2.3 Pneumonia Reporting

Pneumonia will be defined as an event characterized by increased respiratory symptoms (e.g. increased cough, dyspnea, wheezing, purulent sputum), fever (i.e. body temperature greater than 38 °C) or pleuritic chest pain or leukocytosis or other clinical signs consistent with pneumonia considered relevant in the opinion of the investigator and confirmed by X-ray. Any reported pneumonia will have to be confirmed by either X-ray or radiologist reading report of the X-ray (to be kept in the source documents). If not confirmed by X-ray, it should be reported as lower respiratory tract infection.

7.3 Liver safety monitoring

To ensure patient safety and enhance reliability in determining the hepatotoxic potential of an investigational drug, a standardized process for identification, monitoring and evaluation of liver events has to be followed.

The following two categories of abnormalities / adverse events have to be considered during the course of the study:

- Liver laboratory triggers, which will require repeated assessments of the abnormal laboratory parameter
- Liver events, which will require close observation, follow-up monitoring and completion of the standard base liver CRF pages

Please refer to [Table 13-1](#) in [Appendix 9](#) for complete definitions of liver laboratory triggers and liver events

Every liver laboratory trigger or liver event as defined in [Table 13-1](#) of [Appendix 9](#) should be followed up by the investigator or designated personal at the trial site as summarized below. Detailed information is outlined in [Table 13-2](#) in [Appendix 9](#).

For the liver laboratory trigger:

- Repeating the LFT within the next week to confirm elevation.

These LFT repeats should be performed using the central laboratory if possible. If this is not possible, then the repeats can be performed at a local laboratory to monitor the safety of the patient. Repeats laboratory should then be performed at central laboratory as soon as possible. If a liver event is subsequently reported, any local LFTs previously conducted that are associated with this event should be reported on the Liver CRF pages.

- If the elevation is confirmed, close observation of the patient will be initiated, including consideration of treatment interruption if deemed appropriate.

For the liver events:

- Repeating the LFT to confirm elevation as appropriate
- Discontinuation of the investigational drug if appropriate
- Hospitalization of the patient if appropriate
- A causality assessment of the liver event via exclusion of alternative causes (e.g., disease, co-medications)
- An investigation of the liver event which needs to be followed until resolution.

These investigations can include serology tests, imaging and pathology assessments, hepatologist's consultancy, based on investigator's discretion. All follow-up information, and the procedures performed should be recorded on appropriate CRF pages, including the liver event overview CRF pages.

7.4 Pregnancy reporting

To ensure patient safety, each pregnancy occurring while the patient is on study treatment must be reported to Novartis within 24 hours of learning of its occurrence. The pregnancy should be followed up for 3 months after the birth to determine outcome, including spontaneous or voluntary termination, details of the birth, and the presence or absence of any birth defects, congenital abnormalities, or maternal and/or newborn complications.

Pregnancy should be recorded on the Pharmacovigilance Pregnancy Form and reported by the investigator to the local Novartis Drug Safety and Epidemiology Department. Pregnancy follow-up should be recorded on the same form and should include an assessment of the possible relationship to the investigational/study treatment.

Any SAE experienced during the pregnancy and unrelated to the pregnancy must be reported on a SAE form.

8 Data review and database management

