At Visit 102 patients whose eligibility is confirmed will be randomized to one of the five treatment groups with an equal (1:1:1:1:1) randomization ratio:

- QMF149 150/160 µg delivered via Concept1 o.d.
- QMF149 150/320 µg delivered via Concept1 o.d.
- MF 400 µg o.d. delivered via Twisthaler[®]
- MF 800 µg (as 400 µg b.i.d.) delivered via Twisthaler[®]
- Salmeterol xinafoate /fluticasone propionate 50/500 µg b.i.d. delivered via Accuhaler[®]

Visits 102 and 201 take place sequentially on the same date. The assessments at Visit 102 should be performed prior to administration of the first dose of study medication. Randomized patients will enter the 52 week treatment epoch during which they will be required to inhale study medication via Concept1 once daily in the evening (between 5:00 and 8:00 pm) and twice daily via Twisthaler[®] or Accuhaler[®] once in the morning (between 5:00 and 8:00 am) and once in the evening 12 hours after the morning dose (between 5:00 and 8:00 pm).

[figure not shown]
Patients will be followed at regular intervals throughout the 52 week treatment epoch to assess the safety and efficacy of treatment, either by telephone or at clinic visits. Clinic visits are scheduled to take place after 4, 12, 26, 36 and 52 weeks. All clinic visits should occur as scheduled on the Table 6-1. For Visit 214 (Week 52), in case of logistical issues, the visit is allowed to take place within a 4 day window. All patients will be required to attend the clinic visits to perform trough measurements of lung function (24 hours post dosing) after the first dose of study medication (Visit 201) and after the dose of study medication administered at the clinic after 26 and 52 weeks of treatment (Clinic Visit (CV) 207 and 214). Telephone reviews of patients' status will be conducted after 8, 16, 20, 28, 32, 40, 44 and 48 weeks of treatment. Telephone contacts with patients may indicate that a clinic visit is necessary, in which case an unscheduled clinic visit should be arranged as soon as possible and should include safety assessment (AEs, concomitant medications review and unscheduled laboratory exams as appropriate).

A final telephone contact must be conducted at 30-days after last treatment date (telephone visit 301 or unscheduled visit safety call for patients who discontinue treatment earlier than 52 weeks).

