32. Women of child-bearing potential, defined as all women physiologically capable of becoming pregnant, unless they are using highly effective methods of contraception during dosing of study treatment and for 30 days after stopping of study treatment

Only the following highly effective contraception methods are permitted:

- Total abstinence (when this is in line with the preferred and usual lifestyle of the subject) if allowed as effective method of contraception according to local regulations. Periodic abstinence (e.g., calendar, ovulation, symptothermal, post-ovulation methods) and withdrawal are not acceptable methods of contraception.
- Female sterilization (have had surgical bilateral oophorectomy with or without hysterectomy), total hysterectomy or tubal ligation at least six weeks before taking study treatment. In case of oophorectomy alone, only when the reproductive status of the woman has been confirmed by follow up hormone level assessment.
- Male sterilization (at least 6 months prior to screening). For female subjects on the study, the vasectomized male partner should be the sole partner for that subject.
- Use of oral, injected or implanted hormonal methods of contraception or other forms of hormonal contraception that have comparable efficacy (failure rate < 1%), for example hormone vaginal ring or transdermal hormone contraception.
- Placement of an intrauterine device (IUD) or intrauterine system (IUS)
In case of use of oral contraception women should have been stable on the same pill for a minimum of 3 months before Visit 201 (Randomization / Start of treatment epoch).

Women are considered post-menopausal and not of child-bearing potential if they have had 12 months of natural (spontaneous) amenorrhea with an appropriate clinical

profile (e.g. age appropriate, history of vasomotor symptoms) or have had surgical bilateral oophorectomy (with or without hysterectomy) or tubal ligation at least six weeks ago. In the case of oophorectomy alone, only when the reproductive status of the woman has been confirmed by follow-up hormone level assessment is she considered not of child-bearing potential.

33. LAMA use within 3 months prior to visit 101

5 Treatment

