5.4.14 Early study termination

The study can be terminated at any time for any reason by Novartis. Should this be necessary, the patient should be seen as soon as possible and treated for a prematurely withdrawn patient. The investigator may be informed of additional procedures to be followed in order to ensure that adequate consideration is given to the protection of the patient's interests. The investigator

will be responsible for informing the Institutional Review Board/Independent Ethics Committee (IRBs/IECs) of the early termination of the trial.

6 Visit schedule and assessments

The study will consist of a screening epoch, a run-in epoch, a 52 week blinded treatment epoch and a follow-up epoch of 30 days after the last treatment.

Table 6-1 lists all the assessments to be performed for the study and indicates with an “X” the visits at which they will be performed. Patients should be seen for all visits on the designated day or as close as possible to that date. A visit window of 4 days is allowed for Visit 214 as described in Section 3.1. All data obtained for these assessments must be supported in the patients’ source documentation.

The following assessments are scheduled to be performed in order as follows: PROs (AQLQ, [REDACTED], ACQ), ECG, pulse rate, blood pressure, blood sample/urine samples, followed by spirometry in a manner that the spirometry measurements occur at the scheduled time point (See Table 6-2 for Timed Assessments). A minimum 3 min rest period from the beginning of ECG assessments to the start of spirometry manoeuvres must be observed at all times. Whenever ECG is to be taken after a succession of spirometry measurements as described in Table 6-2, a minimum 10 min rest period from the end of spirometry maneuvers and the beginning of ECG assessments must be observed.

Whenever other assessments are scheduled at the same time-point, spirometry must take precedence such that it occurs at the scheduled time point or as near as possible. If necessary other assessments (excluding PROs) can be done after spirometry.

[figure not shown]

Table 6-1 Table of assessment

Visit Number	1	101	102	201	202	203 ⁵	204	205 ⁵	206 ⁵	207	208 ⁵	209 ⁵	210	211 ⁵	212 ⁵	213 ⁵	214	EOT Early treatment discontinu ation	Early study discont inuatio n	301 ⁹
Epoch	Screen	Run-In		Treatment														PSW	Follow-up	
Clinic (C) /Telephone (T)	C	C	C	C	C	T	C	T	T	C	T	T	C	T	T	T	C	C	T	T

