Day Number	-28 to - 14*	-14	1	1/2	30	57	86	113	141	183/ 184	197	225	254	281	309	337	364/ 365 ⁶			395
AQLQ-S+12 ³			X		X		X			X			X				X			
Telephone patient 1 day in advance of visit				S	S		S			S			S				S			
Record healthcare visits for asthma worsening					X	X	X	X	X	X	X	X	X	X	X	X	X	X	X	

Visit early study discontinuation should be used for Premature study withdrawal (please refer to [Section 5.4.10](#) and [Section 5.4.11](#))

*: Time between Visit 1 and 101 can be adapted according to the required wash-out from previous medication listed in [Table 5-2](#)

S These assessments are source documentation only and will not be entered into the e-CRF

X assessment to be reported in the clinical database

¹ For females of child-bearing potential only unless surgically sterile. Additional pregnancy testing might be performed if requested by local requirements

█

³ All PROs assessed at Clinic should be completed before any other assessment. When a scheduled visit is planned on 2 consecutive days the PROs are to be completed on the first day.

⁴ Device training at Visit 1 is for e-diary/peak flow meter. Device training at Visit 102 is for Concept1, Twisthaler[®] and Accuhaler[®]. The diary is an electronic device and the questionnaires and other assessments are based on asthma symptoms

⁵ Site to call patient at specified timepoints in between clinic visits to check if patient asthma symptoms have worsened, any treatment required and e-diary completed accordingly. In case of an asthma exacerbation, the patient should be encouraged by the site to contact it for advice. If necessary, an unscheduled visit to the site may be organized and should capture AEs/SAEs, concomitant medication and safety laboratory exams as appropriate.

⁶ The last dose of study medication will be taken on day 365 in the morning (Visit 214)

■ [REDACTED]

⁹ Information about patients' survival will be obtained by a telephone call during the study treatment period and 30 days after the patient's last dose of study drug for completed patients. For patients who withdraw early, please refer to discontinuation of study treatment and premature patient withdrawal section

¹⁰ If reversibility fails on the first attempt as well as on the repeat, historical reversibility or bronchoprovocation would be acceptable as specified in [Section 4.1](#)

[REDACTED]

Table 6-2 Timed Assessment**

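### Mandatory pregnancy reporting stops with study treatment, 30 days before the protocol's contraception requirement ends

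*Protocol*

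**What the plan says.** Four parts of the protocol bear on this.

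- **Reporting (Section 7.4).** The duty is that "each pregnancy occurring while the patient is on study treatment must be reported to Novartis within 24 hours of learning of its occurrence". The next sentence sets the follow-up: "The pregnancy should be followed up for 3 months after the birth to determine outcome".
- **Contraception (Section 4.2, criterion 32).** Women of child-bearing potential must use "highly effective methods of contraception during dosing of study treatment and for 30 days after stopping of study treatment".
- **Testing (Section 6.5.7, Tables 5-5 and 6-1).** The scheduled tests end at Visit 214 or the early treatment discontinuation visit. Section 6.5.7 deals with "A positive plasma pregnancy test at Visit 1, Visit 101, Visit 102, Visit 207 (Week 26), Visit 214 or EOT", and with a positive result at any other time in the study. The action it requires is to stop study treatment. For further detail it sends the reader to Sections 5.4.9 and 7.4.
- **After the last dose (Sections 3.1 and 6).** The study includes "a follow-up epoch of 30 days after the last treatment", and Section 3.1 adds: "A final telephone contact must be conducted at 30-days after last treatment date". Table 6-1 lists adverse events, serious adverse events, exacerbations, surgery and procedures, and survival at Visit 301. Table 5-5 has a similar list for the 30-day safety call after early discontinuation. Neither table lists a pregnancy test or question at these contacts.

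The SAP contains no rule on pregnancy.

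**The concern.** The protocol asks women to avoid pregnancy for dosing plus 30 days, but obliges sites to report a pregnancy only if it occurs during treatment. Suppose a woman conceives 10 days after her last dose and mentions it at the 30-day call. She has become pregnant inside the contraception period, yet Section 7.4 read literally does not require the site to report the pregnancy or follow it.

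At stake is the completeness of a small body of safety data. Section 10.2 tells women that treatment may carry unknown risks to the fetus if they become pregnant during the study, and under Section 5.4.13 the study runs to Visit 301. Pregnancies in a trial like this are few, so each outcome left uncollected is a noticeable share of what could be learned.

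**Working it through.** No figure in the plan needs reproducing. The check compares two windows, looks for any other rule that would close the gap, and sizes it.

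**1. The two windows, for a completer.** Table 6-1 (footnote 6) puts the last dose on the morning of Day 365.
- Contraception: Day 1 to Day 365 + 30 = Day 395, which is also the day of Visit 301.
- Mandatory pregnancy reporting: ends with treatment, Day 365. The glossary's wider meaning of study treatment, which takes in run-in and background drugs, does not move this end. Section 5.4.3.2 has rescue medication ending at Visit 214 as well.
- Difference: 395 − 365 = 30 days, and 30/395 = 7.6% of the contraception window.

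A woman who stops early has the same 30 days after her own last dose, as a larger share of a shorter window.

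**2. Other rules that might close the gap.**
- *Section 6.5.7* reaches any time in the study, but its action is stopping treatment and it defers to Section 7.4. It adds no reporting duty of its own.
- *Serious adverse events (Sections 7.2.1 and 7.2.2).* Pregnancy is not a seriousness criterion; a birth defect is. Collection runs to 30 days after the last dose or last visit, whichever is later. If Visit 301 counts as the last visit, that is Day 395 + 30 = Day 425. A birth following a conception after Day 365 would normally come well after that. From then on an event is reported only if the investigator suspects that treatment caused it.
- *Adverse event enquiry (Section 7.1)* is by non-directive questioning, so a pregnancy may be volunteered but is not asked about.

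**3. Which conceptions fall in the gap.** Criterion 31 counts pregnancy from conception. A conception on treatment is therefore a pregnancy on treatment, and the 24 hours in Section 7.4 start when the site learns of it. It stays reportable, with full follow-up, even if it is discovered after the last dose. Only conceptions after the last dose are uncovered.

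**4. Expected number.** Two inputs are assumptions:
- 600 to 1,200 of the 2,000 patients are women of child-bearing potential. The protocol gives no number.
- Contraceptive failure is up to 1% per year. Criterion 32 mentions a rate below 1%, but for hormonal methods and without a time unit.

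Woman-years in the gap = women × 30/365.25:
- 600 × 30/365.25 = 49
- 1,200 × 30/365.25 = 99

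Expected pregnancies = woman-years × 0.01:
- 49 × 0.01 = 0.5
- 99 × 0.01 = 1.0

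**The case against.** The best reply is that the protocol leaves less uncovered than the first sentence of Section 7.4 suggests.

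- The second paragraph of Section 7.4 asks for pregnancies to be entered on the pregnancy form and reported, without repeating the on-treatment limit. Section 6.5.7 points to Section 7.4 after speaking of a positive test at any time in the study. Together these allow a wider reading, but they do not settle it. The one sentence that defines which pregnancies must be reported still says on treatment.
- The safety contacts do take place, and adverse events, serious adverse events and procedures are reviewed at them. Section 7.1 also has patients told to report later events thought to be related to treatment. This net is real but partial: it can bring a pregnancy to light without obliging anyone to report or follow it.
- Reporting periods need not match contraception periods; that is a policy choice. This is fair, but the protocol gives no reason for the difference.

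A reader might be tempted to go further in three ways that the documents do not support. The first is that late on-treatment conceptions, too early for the last test, escape reporting. They do not, for the reason in step 3, although no scheduled contact after Visit 214 or early discontinuation asks about them. The second is that outcome data are lost. What is missing is a mandatory trigger; voluntary reporting is not barred and the serious adverse event route stays open. The third is that the protocol itself declares the 30 days a period of fetal risk. Criterion 32 sets a contraception rule and gives no rationale for its length, so that label would be an inference.

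**Conclusion.** The inconsistency stands in the current text, in a narrow form. A conception in the 30 days after the last dose falls inside the contraception period but outside any clear duty to report or follow the pregnancy, and the other safety rules only partly make up for this.

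The size is small: 30 days per woman, and about one expected pregnancy or fewer across the trial. That count depends wholly on the two assumptions in step 4 and scales in proportion to each. The mismatch between the sections does not depend on them. Severity is minor: randomization, endpoints, estimands and analyses are untouched.

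**What to change.** Reconcile Section 7.4 with criterion 32. In Section 7.4, require reporting of any pregnancy occurring from the first dose of study treatment until 30 days after the last dose, with the same follow-up to three months after birth. Keep the glossary meaning of study treatment, so that the change lengthens the window at its end without shortening it at its start.

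In Tables 5-5 and 6-1, add a pregnancy question for women of child-bearing potential at the 30-day safety call and at Visit 301. This would also pick up conceptions late in treatment, which are already reportable but which no later contact asks about.

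The cost is one amended sentence and one question in telephone contacts already scheduled. No visit, test or analysis is added.
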